6.6 Post-Treatment

Cold compresses or chilled gel pack may be applied to the treatment area immediately after treatment to reduce swelling and discomfort. If a blister or greying of skin develops, the area will be treated using standard wound care methods. Subjects will be directed to avoid heat (hot tubs, saunas, etc.) and skin irritant products (products containing tretinoin, retinol, benzoyl peroxide, glycolic/salicylic acids, astringents, etc.) for 1 – 2 days after treatment. At the discretion of the Investigator, subjects may be asked to apply post-treatment products to help minimize skin reactions such as a topical steroid (such as Hydrocortisone Cream) or a skin care lightening agents (such as Tri-Luma® or Hydroquinone Cream) during the course of treatment and post-treatment follow-up period. In the event that any of the skin reactions is excessive or prolonged or unanticipated adverse events occur, additional follow-up visits may be scheduled as deemed appropriate by the investigator. Any additional visits will be recorded and skin condition assessed.

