Clinical Research Protocol

Protocol Title: Evaluation of the Lutronic PicoPlus for the treatment of dermatological conditions such as unwanted tattoos and benign pigmented lesions

Protocol Number: L16004

Version: 5.0

Date: May 23, 2019

Sponsor: Lutronic Global
[name]
[name]
Contact: [name], MBA
[contact]

Principal Investigators
[name]
[name], MBA
[name]
[name]
[name]
[name], PhD
[name]
[name]
[name]
[name], DO
[name]

Table of Contents

Table of Contents

1	Objective	3
2	Non-Significant Risk Determination.....	3
3	Study Device	3
3.1	Device Description	3
3.2	Background	5
4	Study Population	6
4.1	Inclusion Criteria.....	6
4.2	Exclusion Criteria	6
5	Study Design	7
5.1	Number of Subjects.....	7
5.2	Study Design.....	7
5.2.1	Group A Treatment Plan	8
5.2.2	Group B Treatment Plan	8
5.3	Investigational Sites	9
5.4	Study Duration.....	10
6	Study Treatment	10
6.1	Pre-Treatment	10
6.2	Anesthesia.....	10
6.3	Analgesic and anxiolytic oral medications.....	11
6.4	Biopsies.....	11
6.5	Study Treatment.....	11
6.6	Post-Treatment.....	12
6.7	Follow-Up Visits.....	12
7	Institutional Review Board Review	12
8	Informed Consent	13
9	Study Outcomes.....	13
10	Risks and Benefits	13
10.1	Potential Risks	13
10.2	Potential Benefits	14
11	Adverse Events	14
12	Subject Accountability.....	16
13	Records and Reporting	16
14	Confidentiality	16
15	Subject Payment	16
16	References.....	16
17	Appendix A. Patient Satisfaction Questionnaire.....	18
18	Appendix B: Clinician Grading Scales	19
18.1	Investigator's Global Assessment of Improvement.....	19
18.2	Subject's Global Assessment of Improvement.....	19
18.3	Subject Satisfaction Assessment.....	19
18.4	Blinded Reviewer's Global Assessment of Improvement	19
18.5	Melasma Area Severity Index (MASI).....	20

1 Objective

The objective of this investigation is to evaluate the Lutronic PicoPlus for the treatment of dermatological conditions, such as, but not limited to, unwanted tattoos and benign pigmented lesions. The primary objective is to evaluate the capability of the technology to remove unwanted tattoos and benign pigmented lesion including melasma. In this pilot protocol, the PicoPlus treatment may be compared to other commercially available medical laser devices as part of this study.

2 Non-Significant Risk Determination

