5.2 Study Design

The study design is a multicenter exploratory, open-label, clinical trial comparing each subject's condition before to after treatment. Subjects will be selected and assigned to Group A for treatment of unwanted tattoos and Group B for treatment of unwanted benign pigmented lesions, melasma or other skin conditions such as skin rejuvenation.

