6.1 Pre-Treatment

Prior to the first treatment, the Investigator or his/her designee will obtain a medical history for each subject and determine study eligibility in accordance with the Inclusion and Exclusion Criteria specific to this protocol. Subjects will be directed to not use self-tanners within the target treatment area for at least 4 weeks prior to treatment and to avoid using harsh skin treatments such as depilatories, abrasive cleansers, etc. for 1-2 weeks prior to treatment. If the patient is a female capable of pregnancy, a urinary pregnancy test will be performed prior to study participation to determine if she is pregnant. If the result of the test is positive or if the female is breast feeding, she is not eligible to participate in study. The treatment area can be on the face, chest arms, legs or body. High-resolution digital photographs will be taken before and after each treatment. The pre-treatment photo will serve as the baseline for comparison to follow-up photos to assess safety and efficacy. Skin instrumental measures may be taken with standard devices such as DSM II colorimeter (Cortex Technology, Hadsund, Denmark). Other instruments may measure skin properties or visualize the skin using an ultrasound device. Prior to each subsequent treatment, the investigator or his/her designee will review and update the medical condition and compliance with inclusion and exclusion criteria. The clinician will evaluate and grade the skin condition before each treatment and insure that the area has recovered suitably from the prior treatment(s) before proceeding to further treatments. In the event that treatment is delayed the investigator will record the specific skin condition and have subjects return after an additional 1 to 4 weeks for reassessment and subsequent treatments.

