9.1 Standardized methods

Standardized photographs and clinician grading scales will be obtained at baseline and follow-up visits. Camera angle, distance and lighting conditions will be controlled to insure consistency for before and after photographs.

Primary Outcome Measures:

The primary outcome measures that will be analyzed include qualitative clinician grading assessment of improvement as well as patient self-assessed satisfaction. Secondary measures may include colorimeter measurements of changes in skin color and/or other instruments to measure skin properties or visualize the skin using an ultrasound device.

10 Risks and Benefits

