18.1 Investigator's Global Assessment of Improvement

At 6 to 12 weeks (24 weeks optional for tattoo removal) post-final treatment as applicable, the Investigator will be asked to rate the degree of tattoo clearing or reduction in benign pigmentation observed in the subject's treated area using the Physician's Global Assessment of Improvement Scale:

- 3 = Very Significant or Complete Clearing (75 – 100%)
- 2 = Significant Clearing (50 – 74%)
- 1 = Moderate Clearing (25 – 49%)
- 0 = Mild or No Clearing (0 – 24%)

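### Section 6.6 lets pigmented-lesion and melasma subjects use skin-lightening agents right up to efficacy grading, so improvement in users cannot be credited to the laser alone

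*Protocol*

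**What the plan says.** Section 6.6 states: "At the discretion of the Investigator, subjects may be asked to apply post-treatment products to help minimize skin reactions". The products it names are a topical steroid and lightening agents, the latter being Tri-Luma or "Hydroquinone Cream) during the course of treatment and post-treatment follow-up period". It does not distinguish Group A from Group B, limits neither dose nor duration, and sets no stop before efficacy grading.

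The rest of the protocol fixes what is measured and against what:

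- Section 1: "The primary objective is to evaluate the capability of the technology to remove unwanted tattoos and benign pigmented lesion including melasma".
- Section 9.1: "The primary outcome measures that will be analyzed include qualitative clinician grading assessment of improvement as well as patient self-assessed satisfaction". Possible secondary measures include "colorimeter measurements of changes in skin color".
- Section 18.1: "the Investigator will be asked to rate the degree of tattoo clearing or reduction in benign pigmentation", on a scale of 0 to 3. Section 18.5 adds the MASI for melasma, which scores area, darkness and homogeneity.
- Section 6.1: "The pre-treatment photo will serve as the baseline for comparison to follow-up photos to assess safety and efficacy".
- Section 5.2: an exploratory, open-label study that compares each subject's "condition before to after treatment".
- Section 4.2: pigmented-lesion and melasma subjects are excluded if they used hydroquinone or another lightening medication in the 6 months before entry.

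**The concern.** The agents that 6.6 permits act on the quantity being graded. By the protocol's own description they lighten skin, and for pigmented lesions and melasma the efficacy grade is how much pigment has gone. A subject who uses one receives two active treatments on the same outcome, and the single before-after comparison cannot divide the result between them.

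Use is discretionary, so it may differ between sites. It is also likely to be commoner in subjects who darken after treatment, which 10.1 lists as an expected side effect. In such a subject, part of the agent's effect may offset the laser reaction and part may lighten the target lesion, and one grade cannot tell these apart. At stake is whether the pigment half of the primary objective, which concerns what the laser can do, can be answered from subjects who used an agent.

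**Working it through.** **1. Sections set side by side.**

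| Question | Protocol | Consequence |
|---|---|---|
| Who may receive an agent? | 6.6: subjects, without restriction by group | Pigment and melasma subjects are included |
| When? | 6.6: through treatment and follow-up | No washout before grading |
| When is efficacy graded? | 6.7: at 1 to 3 months after the last treatment; Appendix B: at 6 to 12 weeks, with an optional 24 weeks for the MASI | Grading falls inside the permitted period |
| What is graded? | 18.1, 18.5, 9.1: pigment reduction, MASI, skin colour | The agent acts on the same quantity |
| Against what? | 5.2, 6.1: the subject's own baseline; 6.5: optional other lasers only | Nothing isolates the agent's effect |
| Does blinding help? | 18.4, 18.5: blinded photo grading | No; the agent's lightening is in the photograph |

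**2. Length of the permitted window.** This is calendar time in which an agent is allowed, not actual exposure.

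Weeks from first treatment to grading = (treatments − 1) × interval + time to grading. One month is taken as about 4.3 weeks and three months as about 13 weeks. Inputs come from 5.2.2 and Table 2 (typically 2 to 4 treatments at 3 to 5 weeks; limits 1 to 8 treatments, intervals up to 12 weeks), 6.7 and 18.5.

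- Typical, low: (2 − 1) × 3 + 4.3 = 7.3, about 7 weeks.
- Typical, high: (4 − 1) × 5 + 13 = 28 weeks.
- Limit, low: (1 − 1) × interval + 4.3 = 4.3, about 4 weeks.
- Limit, high: (8 − 1) × 12 + 24 = 108 weeks, using the optional 24-week MASI.

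With the 6 to 12 weeks of 18.1 in place of the 1 to 3 months of 6.7, the typical range is (2 − 1) × 3 + 6 = 9 to (4 − 1) × 5 + 12 = 27 weeks. The limits for the clinician grade become 6 weeks and (8 − 1) × 12 + 12 = 96 weeks. The conclusion does not change.

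Off-face intervals are somewhat longer (5.2.2). Each delay adds 1 to 4 weeks (6.1), and a later discretionary efficacy visit would extend the window further.

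**3. Relation to 4.2 and 6.1.** Section 6.1 re-checks eligibility before each later treatment. The 4.2 bullet on lightening agents reads most naturally as an entry rule, because the bullet on other devices adds that it also applies during the study and this one does not. Read literally at the re-check, however, a subject given an agent after one treatment would fail at the next: the gap is at most 12 weeks, or 12 + 4 = 16 with one longest delay, against a look-back of about 26 weeks. This is an ambiguity, not a contradiction. It is no safeguard either, since no re-check follows the last treatment.

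**4. Size of the bias.** If a share *u* of pigment subjects use an agent that changes the probability of a given grade by *d*, the pooled proportion shifts by *u* × *d*. The protocol gives neither quantity and the design cannot estimate *d*, so no range is put forward.

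**The case against.** The strongest reply is that this is an exploratory pilot with no test, success threshold or laser-only estimate. Settings, number of sessions and intervals are already left to the investigator, so grading under usual post-care is a legitimate choice. The products are offered to limit skin reactions, not to treat the lesion, and uptake may be low. Hyperpigmentation can be permanent (10.1) and Group B admits skin types up to IV, so giving up preventive use has a safety cost. Rescue use would remain confounded, and reporting by use is ordinarily a matter for the analysis plan. Section 4.2 gives no reason for its exclusion, and the same bullet also lists retinoids and light-sensitive medication.

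Several of these points stand. The design already limits attribution, uptake is unknown and the remedy is partial. The 4.2 exclusion supports the argument but does not prove that the authors saw these agents as confounders.

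They do not remove the problem. The purpose for which a lightening agent is given does not limit what it does to pigment, and 6.6 itself describes these products as lightening agents, so the argument does not depend on 4.2. Weak attribution from lack of a control is no reason to add a second active treatment that could be avoided. The permission is fixed in the protocol, and no later analysis can recover a laser-only effect in subjects who used an agent. How Group B will be summarised may well be set out in an analysis plan, and its absence here is not held against the protocol.

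**Conclusion.** The concern holds and should be fixed. In pigmented-lesion and melasma subjects who use a lightening agent, the clinician grade, the MASI and any colorimeter change measure laser plus agent. The same applies to any Group B pigment summary that includes them. It does not apply to non-users or to tattoo clearing in Group A.

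The bias is of unknown size. The window in which use is permitted runs for the whole interval to grading: about 7 to 28 weeks on the typical Group B schedule and about 4 to 108 weeks at the limits, before delays. The conclusion rests on the protocol's own description of the products as lightening agents and on at least some Group B pigment subjects being given one. If none are, nothing is lost.

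**What to change.** - Amend 6.6 so that pigmented-lesion and melasma subjects receive no lightening agent before the final efficacy assessment, except as rescue for documented post-treatment hyperpigmentation. Topical steroid and cooling stay available.
- Record product, start date and stop date at the medical history review that Table 3 already schedules at each subject visit.
- Add one sentence stating that such rescue use does not breach 4.2 at the 6.1 re-check.
- Report Group B pigment grades and MASI overall, and descriptively for non-users and for users (labelled as laser plus lightening agent), keeping every observed grade.

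The cost is a change of wording in 6.6, one clarifying sentence and three recorded items within an existing procedure. Preventive use is given up in these subjects, a real if limited clinical concession. The change reduces the confounding but does not remove it, because rescue users remain confounded. The split by use is small, non-randomised and descriptive only, and the non-user result should not be read as an unbiased laser-only effect.

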6.7 Follow-Up Visits

Subjects may be scheduled to return for a follow-up visit 1-2 weeks after the first treatment to assess skin safety and skin reactions to treatment. An additional treatment may be performed as well at this visit. To complete the study subjects must return for a follow-up visit 1-3 months after their last treatment to assess safety and efficacy. Clinician grading, patient satisfaction, and standardized photographic methods will be used at the 1-3 month follow-up visit. At the Investigator's discretion, the subject may be asked to return for a later follow-up visit to reassess safety and efficacy.

7 Institutional Review Board Review

All investigational sites in this study will receive approval by local or independent Institutional Review Board (IRB) prior to starting the study.

Sites allowed to use an independent IRB will be reviewed by:

Allendale Investigational Review Board

[name]
[name]
[contact]
Chairperson: [name]

8 Informed Consent

Signed informed consent will be obtained from all subjects by the Investigator or his/her designee prior to participation in this study.

9 Study Outcomes

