5.2.1 Group A Treatment Plan

Subjects receiving treatment for unwanted tattoos (Group A) will receive 1 - 8 treatments (typically 3 – 5) at 2 - 12 week intervals (typically 6- 8 week) with an optional follow-up visit 1-2 weeks after the first treatment for safety evaluation and a final follow-up 1-3 months after the last treatment for safety and efficacy evaluation. At the discretion of the Investigators, additional follow-up visits may take place to observe the time course of reactions after treatment and/or to assess efficacy (i.e. 6 month follow-up). Table 2 summarizes the visit schedule and Table 3 summarizes the study event schedule. The screening/pre-treatment visit and first treatment visit may occur on same day.

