5.2.2 Group B Treatment Plan

Subjects receiving treatment for unwanted benign pigmented lesions or other dermatological condition such as skin rejuvenation (Group B) will receive 1 - 8 treatments (typically 2 – 4) at 1 – 12 week intervals. For facial treatments the typical interval is 3 – 5 weeks and for off-face the interval is typically a little longer. Subjects may have an optional follow-up visit 1-2 weeks after the first treatment for safety evaluation and at least one final follow-up visit 1-3 months after the last treatment for safety and efficacy evaluation. At the discretion of the Investigators, additional follow-up visits may take place to observe the time course of reactions after treatment and/or to assess efficacy. Table 2 summarizes the visit schedule and Table 3 summarizes the study event schedule. The screening/pre-treatment visit and first treatment visit may occur on same day.

Table 2. Study Visit Schedule

Visit	Group A Tattoo	Group B Pigment and other conditions
Evaluation	1	1
Treatment	1 to 8 treatments Typically 3-5	1 to 8 treatments Typically 2-4
	Typically at 6 -8 week interval, but PI could schedule at 2 to 12 weeks interval	Typically at 3 - 5 week interval, but PI could schedule at 1 to 12 weeks interval
Follow-up	1 at least 3 months after last treatment 2 nd follow-up 6mo	1 - 3 months after last treatment

Table 3. Study Event Schedule

Procedures	Site Initiation	Screen / PreTx Evaluation	1st Tx Visit	Optional 1 – 2 wk safety evaluation	2nd Tx Visit	3rd Tx Visit, etc.	1 - 3 month follow-up visits (s)
Review protocol & study requirements	x						

Inclusion / Exclusion		x					
Med History Review		x	x	x	x	x	x
ICF		x					
Pre-Treatment Skin Evaluation		x	x	x	x	x	x
Laser Treatment			x		x	x	
Immediate Post-Tx Skin Evaluation			x		x	x	
Pre-Tx Clinical Photos			x	x	x	x	x
Post-tx Photos			x	x	x	x	
Patient Satisfaction Questionnaire							x

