10.1 Potential Risks

There is a risk of adverse events, skin reactions or side effects. Expected side effects include:

- Discomfort. Mild discomfort is typical during the treatment of benign pigmented lesions. For tattoo removal treatments, where higher settings are typically used, moderate to significant discomfort is frequently reported. Most patients describe the discomfort as less than when the tattoo was applied. Some areas are more sensitive than others.
- Edema and erythema. Swelling and redness often occur, but will subside in 2-5 days and can be reduced with regular ice application.
- Purpura. The area may appear to be bruised after treatment. The bruising will typically fade in 5-7 days.
- Texture changes. Transient texture changes are often noted, but usually resolve with time. Blisters/scabs/crusting. These may occur and usually take 4-10 days to heal and up to 2 weeks for off-face treatments.
- Petechia or pinpoint bleeding. For tattoo removal treatments, pinpoint bleeding or

- oozing may develop and can continue up to 2 days post-treatment. Pinpoint bleeding is less common during treatment of benign pigmented lesions but may develop and will typically resolve within a few hours post-treatment.
- Hyper/hypopigmentation. Skin can develop temporary lightening or darkening after laser treatment. Hyperpigmentation can be worsened with sun exposure. Hypopigmentation usually occurs after multiple treatments. Pigmentary issues typically resolve with time, but can be permanent.
 - Allergic reaction. Patients who have had a prior allergic reaction to ink during tattoo application may have a similar reaction after laser treatment. This reaction can be controlled by a pre-treatment and/or post-treatment regimen of steroids and antihistamines.
 - Infection. Despite good wound care, pain, swelling, oozing, and fever can indicate the development of an infection. Topical and/or oral antibiotics may be necessary.
 - Scarring. Scarring is a rare occurrence, but it is a possibility if the skin's surface is disrupted. To minimize the chances of scarring, it is important that patients follow all post-treatment instructions provided by their healthcare provider. Good post-treatment care can help reduce the possibility of scarring.
 - Darkening of lesions. Lesions will darken post-treatment and will slough 5-21 days post-treatment.

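### Section 6.7 allows a further treatment at the optional visit 1-2 weeks after the first, which conflicts with Group A's 2-week minimum interval and, for both groups, with Table 3.

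*Protocol*

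**What the plan says.** Section 6.7 (Follow-Up Visits) applies to all subjects. It sets out the early visit: "Subjects may be scheduled to return for a follow-up visit 1-2 weeks after the first treatment to assess skin safety and skin reactions to treatment". The next sentence reads: "An additional treatment may be performed as well at this visit". Neither sentence separates Group A from Group B.

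Section 5.2.1 places Group A treatments "at 2 - 12 week intervals (typically 6- 8 week" apart, and describes the same early visit as an "optional follow-up visit 1-2 weeks after the first treatment for safety evaluation". It mentions no treatment at that visit. Table 2 repeats the Group A range as the limit of the investigator's discretion: "PI could schedule at 2 to 12 weeks interval".

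Section 5.2.2 gives Group B an interval of 1-12 weeks and the same optional early visit, again for safety evaluation.

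Table 3 gives the early visit its own column, headed as an optional safety evaluation and separate from the second treatment visit. The rows for laser treatment and for the immediate post-treatment skin evaluation are blank in that column. The rows for pre-treatment skin evaluation, pre-treatment photographs and post-treatment photographs are marked.

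Section 6.1 requires the clinician to grade the skin before each treatment and to confirm suitable recovery. If treatment is delayed, the subject returns after a further 1 to 4 weeks.

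**The concern.** Two operative rules on treatment timing disagree for Group A. A site that treats a tattoo subject on day 10 acts within section 6.7 and outside section 5.2.1 and Table 2. In a multicenter study, sites may resolve this differently, and whether a given treatment counts as a deviation then depends on which section is consulted.

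The event schedule adds a second problem, for both groups. A site working from Table 3 finds no laser treatment at this visit. A site that treats there under section 6.7 has no immediate post-treatment skin evaluation scheduled in that column, although Table 3 schedules one at every treatment visit.

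The visit's stated purpose is to observe reactions to the first treatment. A second treatment then can blur whether later reactions belong to the first or the second session. Section 10.1 says of blisters, scabs and crusting: "These may occur and usually take 4-10 days to heal and up to 2 weeks for off-face treatments". The visit can therefore fall before healing is complete, particularly off the face, and section 6.1 allows treatment on the chest, arms, legs or body.

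**Working it through.** No sample size, power or error rate is involved, and the protocol states no figure to reproduce. The check compares the stated windows and then reads Table 3 by column. Weeks are converted at 7 days each, with no visit tolerance, since these sections give none.

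**Step 1. Windows in days after the first treatment**

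| Item | Source | Weeks | Days |
|---|---|---|---|
| Early visit, treatment allowed | 6.7 | 1-2 | 7-14 |
| Group A treatment interval | 5.2.1, Table 2 | 2-12 | 14-84 |
| Group B treatment interval | 5.2.2, Table 2 | 1-12 | 7-84 |

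**Step 2. Overlap with the early visit**

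- Group A: days 7-14 and days 14-84 share day 14 only. The visit window holds 14 − 7 + 1 = 8 whole days, of which 7 (days 7-13) are below the minimum. The largest shortfall is 14 − 7 = 7 days.
- Group B: days 7-14 lie wholly within days 7-84. All 8 days are permitted, so there is no interval conflict.

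**Step 3. Table 3, early visit against second treatment visit**

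| Row | Early visit | Second treatment visit |
|---|---|---|
| Pre-treatment skin evaluation | marked | marked |
| Laser treatment | blank | marked |
| Immediate post-treatment skin evaluation | blank | marked |
| Pre-treatment photographs | marked | marked |
| Post-treatment photographs | marked | marked |

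The early column calls for photographs after a treatment that it does not list. It matches neither a visit without treatment nor a complete treatment visit.

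**Step 4. Recovery times in section 10.1**

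The usual healing time of 4-10 days for blisters, scabs and crusting overlaps the visit on days 7-10. The off-face limit of 2 weeks extends that to day 14. This is context for why the timing rule matters and is not itself a contradiction.

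**The case against.** The strongest reply is that section 6.1 already protects the subject. Grading and suitable recovery are required before every treatment, including one given under section 6.7, so calendar days alone do not decide re-treatment. This stands as a limit on the clinical risk. It does not remove the conflict: a tattoo subject whose skin has recovered by day 10 may be treated under section 6.7 and may not under section 5.2.1.

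Section 6.7 is also only permissive, and a careful site could apply it within each group's interval: the whole window for Group B, day 14 for Group A. That reading is available, but section 6.7 does not state it.

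A visit with treatment might be treated as the second treatment visit, whose Table 3 column is complete. However, section 6.7 places the treatment at the safety visit itself and Table 3 keeps the two apart. Relabelling would still leave a Group A treatment on days 7-13 below the minimum. The marked post-treatment photographs suggest that treatment may have been contemplated and the other marks omitted, which supports correcting the table.

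A reader might infer that reactions after early re-treatment cannot be attributed at all. The protocol does not support that. Table 3 marks a pre-treatment evaluation and photographs at this visit, and section 6.1 requires prior grading, so reactions already present are captured before the laser is used again. Section 11 grades relationship to study treatment, not to a numbered session. Later reactions can be confounded, and the same overlap arises under Group B's permitted 1-week interval.

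A reader might also rely on the section 10.1 statement that "Lesions will darken post-treatment and will slough 5-21 days post-treatment". It does not help the Group A case. It speaks of lesions, which the same list distinguishes from tattoos, and days 5-21 also contain Group A's permitted day 14 and Group B's permitted day 7.

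**Conclusion.** The inconsistency holds, in two parts. For Group A, section 6.7 conflicts with section 5.2.1 and Table 2 on days 7-13 of a day 7-14 window. For both groups, section 6.7 conflicts with the description of the visit as a safety evaluation and with the blank laser-treatment and immediate post-treatment rows in Table 3.

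This rests on three readings: the additional treatment in section 6.7 means laser treatment, its natural sense there; the 2-12 week range is a limit, as Table 2's wording on investigator discretion indicates; and a week is 7 days.

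The number of subjects exposed is unknown. Both the visit and any treatment at it are optional, and the typical Group A interval is 6-8 weeks. Every Group A subject who attends is only a ceiling. It would be wrong to infer that the protocol directs treatment of unhealed skin, because section 6.1 requires recovery first. The point is a contradiction in treatment timing, relevant to safety and cheap to correct, and it should be corrected.

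**What to change.** Reconcile sections 6.7, 5.2.1 and 5.2.2 with Tables 2 and 3 so that each group has one consistent rule on whether treatment may be given at the visit 1-2 weeks after the first treatment.

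- If treatment may be given there, mark the laser-treatment and immediate post-treatment skin evaluation rows in that column of Table 3, by group if the rule differs. State that the section 6.1 pre-treatment grading is recorded before the laser is used.
- If it may not, remove the permission from section 6.7 and review the post-treatment photograph mark in that column.

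Which rule stands is for the sponsor and investigators. The cost is a change of wording and table marks in the next amendment. No assessment needs to be added to the pre-treatment part of the visit, since section 6.1 and Table 3 already require it.
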